Implant Primary Stability and Ridge Dimensional Changes Utilizing the Osseodensification Protocol

NCT05283928

Version Date: 09/12/2023

| | |
|--------------------------------|--|
| Protocol Title: | Implant Primary Stability and Ridge Dimensional Changes Utilizing the Osseodensification Protocol |
| Principal Investigator: | [name] DDS, MS |
| Co-Investigators: | [name] DDS, MS, PhD, [name], BDS, DSc, MDS, [name] DDS, MS, DMSc, [name] |
| Study Coordinator: | [name] and [name] |
| Population: | Twenty patients, 22 years or older, that are not systemically compromised and nonsmoking. |
| Number of Sites: | One |
| Study Duration: | 24 weeks |
| Subject Duration: | 24 weeks |

General Information

Implant stability is critical for the success of osseointegration and for immediate loading protocols. Surgical instrumentation techniques, implant macrogeometric design, bone quantity and quality all affect implant primary stability. In contrast to standard drilling for implant placement, osseodensification drilling compacts and auto-grafts bone at the osteotomy walls resulting in increase of ridge dimension, higher insertion torque, and in increased temporal bone to implant contact even in low density bone.

Background Information

Studies conducted comparing standard drilling (SD) with osseodensification drilling (OD) show significant increase in implant primary and secondary stability with OD. Through surgical compaction of bone into marrow space, OD has been found to increase the insertion torque values regardless of the type of implant surface (machined versus acid-etched implant surfaces).¹ In another study, significantly lower insertion torques have been noted when SD was utilized.² Additionally, through histomorphometric analysis, greater bone-to-implant contact (BIC) and bone area fraction occupancy (BAFO) has been demonstrated with OD.² Autologous bone chips have been recorded with greater frequency in the OD group compared to the SD group.³ The autologous bone chips acted as nucleating surfaces promoting new bone formation resulting in greater implant stability and bone density.³ Another study verified the infrequent presence of bone chips in the SD group compared to the commonly observed presence of bone chips in the OD groups.⁴ When clockwise (CW) and counterclockwise (CCW) OD was compared, higher volume of bone chips was observed in the CCW OD group. Further research has demonstrated increase in ridge dimensions with the OD method. Specifically, narrower ridges measuring 1-3 mm at the crest demonstrated the greatest increase in width accounting for 2.83 ± 0.66 mm increase. Greater changes in ridge width were noted at the crest versus 10 mm from the crest.⁵

Hypothesis:

- Bone Densification protocol does not increase implant primary and secondary stability values in 0-6 wks as compared to standard drilling protocol.
- Bone Densification does not increase ridge dimensions as compared to standard drilling protocol.
- Bone densification does not increase bone volume and density as compared to standard drilling protocol.
- There is no significant difference between bone densification and standard drilling protocols.

Objectives

The aim of this study is to compare ridge dimensional changes between densification and standard drilling protocols. Additionally, primary and secondary stability of implants placed by bone densification and standard drilling protocols will be compared. A comparison of the insertion torque values (measured in Ncm) and temporal (immediate, 3, 6, and 12 weeks) implant stability quotients at osteotomies prepared with standard drilling procedures or when subjected to osseodensification surgical instrumentation will be performed. Dimensional changes will be measured before and after completion of the implant osteotomy, and compared between standard and osseodensification surgical instrumentation. Finally, volumetric changes and ridge dimensional changes will be evaluated between initial CBCT and 6 months follow-up CBCT.

Study Design

Twenty patients (we will try to balance male and female population sample if it is possible) in need to receive at least 2 dental implants in single-unit or larger span edentulous spaces will be selected. Nonsmoking and not systemically compromised patients will be selected. The following scenarios will be chosen to rehabilitate the anterior and posterior regions in this study.

- **If maxilla:**
 - split-mouth, implant insertion to replace anterior or posterior teeth: one side will receive osseodensification drilling instrumentation and the other standard drilling. Site selection is randomized by coin toss.
 - same side, adjacent teeth: Site selection will be randomized by coin toss.
- **If mandible:**
 - split-mouth or same side surgical instrumentations will be performed, as described for maxilla.

Surgical technique

Final implant (NobelReplace® Conical) and respective bur diameter for either osseodensification instrumentation and conventional drilling will be either 3.5 mm, 4.3 mm or 5.0 mm. Implant lengths will be from 8.0 up to 13.0 mm. Versah (Fig. 2) and NobelReplace ® Conical implant surgical kit (Fig. 1) present burs with identical diameter and instrumentation will be performed so last bur diameter matches with chosen implant diameter. When using Versah, counterclockwise drilling will be performed in maxilla, and in mandible clockwise drilling. Before surgery, all patients will receive intraoral scans and will be subjected to tomographic examination of the edentulous site for virtual implant planning, surgical planning, implant selection, and fabrication of a surgical guide with a mark on the buccal aspect identifying the middle of the osteotomy. The osseodensification technique will be used for comparison with conventional drilling regarding ridge dimensional changes measured with a ridge caliber (Krekler Sliding Caliper Round Gauge Dental Instrument) at

implantation (T0); and insertion torque (IT) values and implant stability quotients (ISQ) at implantation (T0), 3 (T1,) 6 (T2), and at 12 weeks (T3). ISQ will be measured with Osstell ISQ meter. Data will be evaluated with paired t-tests. After T0, patients will receive a healing abutment which will be removed and repositioned for T1, T2, and T3 evaluations. After 12 weeks patients will be prosthetically restored if insertion torque was 35 Ncm and/or ISQ values are 68. After 6 months, follow-up tomographic examination will be completed for volumetric analysis.

Study Population

Patients of the Graduate Periodontology clinic requiring implant therapy will be screened and selected to participate in the study based on the following inclusion and exclusion criteria:

Inclusion Criteria

- Adults aged 22 years and older.
- Patients who understand and agree to this study.
- Adequate Oral hygiene
- One or more edentulous spaces, which are 10 weeks or longer after extractions
- Patients requiring signature from a Legally Authorized Representative (LAR) will be eligible to participate in the study

Exclusion criteria:

- Grafted extraction socket or ridge augmentation procedure utilizing xenogenic bone graft material.
- Pregnancy as checked via medical history
- Smoking of more than 5 cigarettes/day.
- History of alcoholism or drug abuse during the last 5 years.
- Uncontrolled Hypertension or diabetes.
- Patient with malignant tumor.
- Patients on daily dose of steroids.
- Patients with history of chemotherapy or radiation for the last 12 months.

Study Procedures

Forty implants will be paired and placed in 20 patients using OsseoDensification (OD) protocol as test, and using standard drilling (SD) protocol as control. Sites will be randomly assigned in comparative patients prior to flap reflection.

Primary Outcome Measures:

All ridge dimensions will be measured immediately after flap reflection and after final osteotomy preparation: at crest, 5 mm and 10 mm apical from the crest. A surgical guide will be fabricated for the implant surgery which will also be marked on the buccal indicating the middle of the osteotomy and the ridge dimensions will be measured using the mark as a standard reference. The measurements will be completed the day of surgery only.

Secondary Outcome Measures:

1. All implants' primary stability will be measured by insertion torque values and by resonance frequency analysis (ISQ) immediately after implant placement (T0). Resonance frequency analysis will be measured at three weeks (T1), six weeks (T2), and twelve weeks (T3) post implant placement.
2. At 6 months all patients will receive CBCT for volumetric analysis.

Digital radiographs (periapical radiographs PA) will be taken prior to implant placement, post placement, and at 6 weeks. Cone beam computer tomography (CBCT) will be obtained prior to implant placement for implant planning and fabrication of a surgical guide, and at 6 months post-implantation for volumetric analysis.

In any incidence of less than 1 mm buccal plate thickness has resulted after bone preparation, bone grafting will be done post implant placement and complete implant coverage will be achieved for two-stage healing protocol. Cases requiring bone grafting will be excluded from the CBCT analysis at 6 months and from 3-week (T1) and 6-week (T2) ISQ readings. Cases requiring two-stage healing will also be excluded from 3-week (T1) and 6-week (T2) ISQ readings, but will be included in 12-week (T3) ISQ readings at second stage surgery.

At 12 weeks all patients will receive dental restorations. Implants' restorative phase will be initiated at any time resonance frequency analysis become equal or more than ISQ 68.

Why 3 weeks, 6 weeks, and 12 weeks ISQ measurements:

The lowest value of implant stability is at three weeks after implant placement and it is most pronounced in type IV bone. (Barewal et al, Int. JOMI 2003. Sep-Oct; 18 (5) 641-51) Implant Stability increases greatly between week 0 and week 6 and showed slow increase between week 6 and 6 months. (Jae-Min Kim et al, J. Adv. Prosthodont 2009. March; 1 (1) 31-36). Implant stability starts declining after first week and reach its lowest value at three week to start increasing in the fourth week. (Markovic et al, OOOOE 2011. November; 112, (5) 557-63) ISQ is obtained at 12 weeks to ensure implant stability prior to having implants restored.

Data and Safety Monitoring

Implant therapy, either with standard drilling or osseodensification, has some inherent possible complications such as post-operative discomfort, infection, pain, implant failure, swelling and bleeding. All clinical protocols currently in effect in the Graduate Periodontology clinic will be followed in order to minimize these risks. Currently, all patients, undergoing implant therapy at the Graduate Periodontology, receive antibiotics prophylactically, pain medications for management of pain and discomfort, steroids as needed to help with edema, and chlorhexidine mouthrinse to maintain the surgical sites clean as possible by reducing the bacterial load. In the event of implant failure, the implant will be removed, and the site will be grafted for future repeat of the implant therapy at the specific area.

Statistics & Computer tomography analysis

Data will be evaluated with paired T-tests. The total number of subjects enrolled in the study will be twenty and all eligible subjects will be provided with the opportunity to participate. Termination of the trial will be considered only when unexplained implant failures are observed, excluding implant failures associated with systemic conditions, infections or other well documented contributing factors in the literature.

1.2-D Linear CBCT analysis: we will superimpose the pre- and post- surgical CBCTs. Then determine a cross-sectional plane that goes through the long axis of the placed implant and is as perpendicular as possible to the buccal/lingual walls for consistent reproduction. We will use the selected cross-sectional plane to measure the overall buccolingual width of the ridge and assess any ridge dimensional changes. The software automatically finds the best fit for superimposition of the CBCT scan which allows for accurate reproducible measurements.

2.3-D Volumetric CBCT analysis: Superimposition of the CBCTs, as previously explained, will be completed first. A box will be used as the region of interest which will encompass the implant and the adjacent cortical plates. The shape of the box will be kept the same for consistency. The segmented ridge volume within the box will be used to get actual volumetric differences. The term segmentation is a radiology term and refers to the inclusion of voxels (in this case, alveolar process) that falls within a specified range of CBCT gray scale values determined by an operator.

Ethics

At the time of initial consult, all eligible subjects will be provided with the opportunity to decide if they want to participate in the study. A description will be provided as well as all that will be required by

the patient. If they agree to participate, a written consent form will be obtained, and the subject will be provided with a copy of the signed consent form. All consent forms will be kept by the Primary Investigator in a locked and secured place.

Data handling and record keeping

All participants will be identified by a number and all identifying information will be kept confidential. All the data will be collected in a spreadsheet (excel document) under the participant's specific number. Only the Primary Investigator will have access to the identifiable information linked to the subject's specific number which will be kept in a locked and secured cabinet in room 6477 in the Department of Periodontics and Dental Hygiene.

Quality control and assurance

[figure not shown]
The primary investigator and all co-investigators participating in the study will be calibrated in order to ensure proper use of the Ostell ISQ meter and Mitutoyo Digimatic Caliper. The Ostell ISQ meter is a device that is used in everyday clinical practice and does not require special training. The Mitutoyo Digimatic Caliper is a digital caliper that measures ridge dimensions with accuracy of two numbers after the decimal point and does not require special training. The surgical techniques and procedures are used on a daily basis and follow all standards of care thus, no special training or calibration is necessary.

Publication Plan

All results from our site will be combined and published in a peer review journal as part of a multicenter study.

ATTACHMENTS

Drill protocols /Product reference lines

Figure

1: Burs

from

the NobelReplace® Conical implant surgical kit. The corresponding 3.5, 4.3 or 5 mm diameter bur from Versah kit will be used for sites where osseodensification will be performed.

For short implant placement, implant major diameter needs to be \leq the bur (average diameter) at the 8mm laser mark. Please refer to page 16 in the Instructions for Use Manual.

In Ridge Expansion cases, please oversize your osteotomy and make sure that the crest diameter is equal to or larger than the implant major diameter.

In Hard Bone (Mandible), after Finishing the Full Osteotomy Preparation, Use the Next Larger Size Densah Bur to the 3mm Laser-Mark Depth to make sure the Osteotomy Crestal Diameter is Equal to or Larger than the Implant Major (Crestal) Diameter.

Use Densah Burs in full-step increments for Sinus Lift cases. Example: 2.0mm, 3.0mm, 4.0mm, 5.0mm

Use large block display to compare Bur identification system when using the schematic below for proper Bur usage

● VT5 Set ○ VT8 Set ● VS8 Set

| Densifying Mode CCW (800-1500) RPMs / Cutting Mode CW (800-1500) RPMs | | | | | | | | | | | | | | | | | |
|--|---------|---------|---|--------------|---------------|---------------|---------------|----------------------|---|-------|--------------|---------------|--------------|---------------|---------------|---------------|---|
| Nobel Biocare® | | | NobelReplace® Tapered, Replace® Select Tapered, NobelReplace® Conical, NobelDirect®, NobelDirect® Posterior, Speedy Groovy® | | | | | | | | | | | | | | |
| | | | Soft Bone | | | | | Hard Bone (Mandible) | | | | | | | | | |
| In densifying mode make sure your osteotomy is 1.0 mm deeper than the actual implant final length. In extreme hard bone, utilize DAC (Densify After Cut) Protocol. Find protocol in IUD. | | | | | | | | | | | | | | | | | |
| Geometry | Major Ø | Minor Ø | Pilot | Bur 1 | Bur 2 | Bur 3 | Bur 4 | Bur 5 | Densah® Bur Block Display | Pilot | Bur 1 | Bur 2 | Bur 3 | Bur 4 | Bur 5 | Bur 6 | Densah® Bur Block Display |
| Taper | 3.0 | 2.5 | Pilot | VT1828 (2.3) | VS2228* (2.5) | — | — | — | ● ● ● ● ● ● ○ ○ ○ ○ ● ○ ○ ○ ○ ● ○ ○ ○ ○ ● ○ ○ ○ ○ | Pilot | VT1828 (2.3) | VS2228* (2.5) | — | — | — | — | ● ● ● ● ● ● ○ ○ ○ ○ ● ○ ○ ○ ○ ● ○ ○ ○ ○ ● ○ ○ ○ ○ |
| Taper | 3.5 | 3.0 | Pilot | VT1525 (2.0) | VT2535* (3.0) | — | — | — | ● ● ● ● ● ● ○ ○ ○ ○ ● ○ ○ ○ ○ ● ○ ○ ○ ○ ● ○ ○ ○ ○ | Pilot | VT1525 (2.0) | VT2535* (3.0) | — | — | — | — | ● ● ● ● ● ● ○ ○ ○ ○ ● ○ ○ ○ ○ ● ○ ○ ○ ○ ● ○ ○ ○ ○ |
| Taper | 4.3 | 3.7 | Pilot | VT1828 (2.3) | VT2838* (3.3) | — | — | — | ● ● ● ● ● ● ○ ○ ○ ○ ● ○ ○ ○ ○ ● ○ ○ ○ ○ ● ○ ○ ○ ○ | Pilot | VT1828 (2.3) | VT2535 (3.0) | VT2838 (3.3) | VS3238* (3.5) | — | — | ● ● ● ● ● ● ○ ○ ○ ○ ● ○ ○ ○ ○ ● ○ ○ ○ ○ ● ○ ○ ○ ○ |
| Taper | 5.0 | 4.2 | Pilot | VT1828 (2.3) | VT2838* (3.3) | VT3545* (4.0) | — | — | ● ● ● ● ● ● ○ ○ ○ ○ ● ○ ○ ○ ○ ● ○ ○ ○ ○ ● ○ ○ ○ ○ | Pilot | VT1828 (2.3) | VT2535 (3.0) | VT2838 (3.3) | VT3545 (4.0) | VT3848* (4.3) | — | ● ● ● ● ● ● ○ ○ ○ ○ ● ○ ○ ○ ○ ● ○ ○ ○ ○ ● ○ ○ ○ ○ |
| Taper | 5.9 | 5.0 | Pilot | VT1525 (2.0) | VT2535 (3.0) | VT3545 (4.0) | VT4555* (5.0) | — | ● ● ● ● ● ● ○ ○ ○ ○ ● ○ ○ ○ ○ ● ○ ○ ○ ○ ● ○ ○ ○ ○ | Pilot | VT1525 (2.0) | VT2535 (3.0) | VT2838 (3.3) | VT3545 (4.0) | VT3848 (4.3) | VT4555* (5.0) | ● ● ● ● ● ● ○ ○ ○ ○ ● ○ ○ ○ ○ ● ○ ○ ○ ○ ● ○ ○ ○ ○ |

*Denotes implant placement.

*Clinician experience and judgment should be used in conjunction with the Densifying Reference Guide recommendation and suggested use protocols.

MD45 REV05

Figure 2: Versah burs to be used per implant diameter for soft and hard bone.

Products to be used in this project.

| Product | Quantity | Check if Requested from Versah |
|---|----------|--------------------------------|
| Osseodensification drills - kit | 4 | X |
| Osstell ISQ | 1 | X |
| Krekler Sliding Caliper Round Gauge Dental Instrument | 1 | |
| NobelReplace® Conical implants and healing abutments | 40 | |
| Computed Tomographic scans | 20 | |

| | | |
|-----------|----------------|--|
| PTFE 4.0 | 20 | |
| Lidocaine | 1 package (50) | |

REFERENCES

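### Hypothesis 3 names bone density but no density outcome is defined, and the operator-set gray range lets compaction count as ridge volume

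*Combined protocol and SAP*

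**What the plan says.** The Hypothesis section lists as a null: "Bone densification does not increase bone volume and density as compared to standard drilling protocol".

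The places where a matching outcome should appear are these:

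- Objectives: "volumetric changes and ridge dimensional changes will be evaluated between initial CBCT and 6 months follow-up CBCT", together with insertion torque, stability quotients and ridge dimensions around the osteotomy.
- Primary Outcome Measures: ridge dimensions at three levels, taken on the day of surgery only.
- Secondary Outcome Measures: insertion torque and ISQ as measures of stability, and "At 6 months all patients will receive CBCT for volumetric analysis".
- Statistics & Computer tomography analysis, item 1 (2-D): use one cross-section to "measure the overall buccolingual width of the ridge and assess any ridge dimensional changes".
- Same section, item 2 (3-D): "The segmented ridge volume within the box will be used to get actual volumetric differences". Segmentation means including the voxels, identified in a parenthesis as alveolar process, whose value "falls within a specified range of CBCT gray scale values determined by an operator".

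The box contains the implant and the neighbouring cortical plates, and its shape is to be held constant. The plan gives no limits for the gray range and does not say whether one range serves both scans, both sites or all patients.

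**The concern.** Two things do not fit together. The hypothesis names two properties, and the plan measures at most one of them. And the measure of that one is built from gray values, which are what a change in density would alter.

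The Background section gives the expected mechanism of the test technique: bone is pressed into marrow spaces, and greater bone density results. A marrow voxel that gains bone can move from below the lower gray limit to above it and then count as ridge volume, although the outer surface of the ridge has not moved. Because this mechanism belongs to the test technique, pairing sites within a patient does not cancel the effect; it goes straight into the paired difference.

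Two misreadings follow. A positive volume test could be reported as rejecting a joint null on volume and density that the design does not test. A change inside the ridge could be reported as a gain in ridge size. The Publication Plan intends to pool the results with other centers, where an operator-chosen range could also differ from center to center.

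**Working it through.** The plan states no effect size, SD or power for volume or density, so it has no figure to reproduce.

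**Step 1: look for a density outcome.** The planned measures are ridge width at surgery, insertion torque, ISQ, CBCT buccolingual width and CBCT segmented volume. Torque and ISQ are presented as stability measures. No mean gray value, density unit, gray-value calibration, bone fraction or histology is defined. Density is one of two quantities in hypothesis 3, and it has no outcome.

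**Step 2: can segmented volume rise with the outer shape fixed?** All gray values here are assumptions. Take 30% cortical voxels (mean 1200, SD 200) and 70% trabecular voxels (mean 350, SD 200), with no upper limit. Shift 25–50% of the trabecular voxels up by 100–200 units. With lower limit L and normal gray values, the fraction counted is

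0.3 × P(cortical > L) + 0.7 × P(trabecular > L).

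Example: L = 300, half the trabecular voxels shifted by 200.

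- Before: 0.3 + 0.7 × 0.599 = 0.719.
- After: 0.3 + 0.7 × (0.5 × 0.599 + 0.5 × 0.894) = 0.823.
- Apparent rise: 0.823/0.719 − 1 = 14.4%.

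| Lower limit | Fraction counted at baseline | Apparent rise in volume |
|---|---|---|
| −200 | 0.998 | 0.0–0.1% |
| 100 | 0.926 | 1.2–3.5% |
| 300 | 0.719 | 4.3–14.4% |
| 400 | 0.581 | 5.9–22.4% |
| 500 | 0.459 | 6.7–28.4% |

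An upper limit of 1500 changes these rises by at most about 1.3 percentage points (28.4% becomes 29.7%). The result is governed by the lower limit, which the plan does not give.

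**Step 3: compare with a real gain.** Assume a region of 7 × 8 × 10 = 560 mm³ and a true width gain of 0.5 mm, which is 0.5 × 8 × 10 = 40 mm³. Assume marrow fills 50–80% of the region and 5% of marrow voxels cross the limit:

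- 50% marrow: 0.05 × 0.50 × 560 = 14 mm³, or 14/40 = 35% of the real gain.
- 80% marrow: 0.05 × 0.80 × 560 = 22.4 mm³, or 56% of it.

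The upper end is generous. A 4.3 × 10 mm implant treated as a cylinder takes π × 2.15² × 10 ≈ 145 mm³, leaving about 415 mm³. The same shares of that remainder give 0.05 × 0.50 × 415 = 10.4 and 0.05 × 0.80 × 415 = 16.6 mm³. Applying 5% to the whole 560 mm³ would give 28 mm³, but that treats cortical bone and implant as marrow and should not be used.

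**The case against.** The best defence is the wording of item 2. It calls the quantity ridge volume, and the parenthesis says that the voxels to be included are the alveolar process. An operator who sets the range to capture the whole ridge gets nearly the outer-contour volume, and the artefact is then close to zero (first row of the table). In the assumed model a limit of 500 would miss more than half of the ridge at baseline, so the largest rises belong to a setting that a careful operator is unlikely to choose. This stands as a reason to call the volume part ambiguous. It does not settle the matter, because the text nowhere requires such a range or the same range for the two scans.

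The 2-D width on the same superimposed scans is a real cross-check: a volume gain with no width gain would be a warning sign. It is partial, being one plane.

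The mechanism may also not act equally everywhere. The Surgical technique section has the osseodensification burs run clockwise in the mandible, while the attached drill chart labels clockwise as the cutting mode. On the documents' own labels, mixing is less certain at mandibular sites.

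A reader might go further and infer that neither half of hypothesis 3 can be answered, or that the volume result will be wrong. The documents do not support that. With an inclusive range the volume half is answerable, and nothing shows which range will be used.

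**Conclusion.** The density part of hypothesis 3 has no outcome and cannot be tested as written. This rests on the text alone. The volume part is open to contamination by density change, because the gray range is operator-set and is not required to be constant across scans and sites.

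The size of that contamination cannot be derived from the documents. Under the assumed gray values it runs from 0.0% to 28.4% of segmented volume, depending mainly on the lower limit. Under the assumed region, marrow share and 5% crossing, it is about 14–22 mm³ against 40 mm³ for a 0.5 mm width gain, and less once the implant's space is taken out. These figures show that the effect could matter; they do not estimate it.

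The affected result is a secondary outcome. The primary ridge measurement at surgery is untouched. The change should be made, but the trial's main comparison does not depend on it.

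**What to change.** 1. Delete density from hypothesis 3. If the sponsor wants to keep it, label it an exploratory comparison of mean gray value in the same region, away from metal artefact.
2. Define ridge volume as all space inside the outer ridge contour, within the fixed box, on both superimposed scans, whatever the contour contains. Gray shifts in the marrow then do not change the volume. Nor does the implant, which is inside the box at follow-up but absent at baseline and whose handling the plan does not state.
3. Prespecify one gray limit for the outer boundary and use it for both scans of a patient and both sites.

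Fixing one range while keeping the voxel count would remove operator discretion, but marrow voxels could still cross the limit; the contour definition is what separates size from density.

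No new scans, visits or patients are needed. The cost is extra contouring on up to 40 sites × 2 scans = 80 readings. The calibration paragraph covers only the ISQ meter and the caliper, so a short reading instruction for the contour should be added. The sponsor also gives up any confirmatory claim about density, which the present plan could not support in any case.

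### In adjacent-site pairs, nothing stops the osseodensification site being drilled between the two ridge readings at the standard-drilling site, so any spillover would bias the primary difference toward zero

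*Combined protocol and SAP*

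**What the plan says.** Under Study Design, a maxillary pair may be split-mouth, where "one side will receive osseodensification drilling instrumentation and the other standard drilling", or it may be "same side, adjacent teeth: Site selection will be randomized by coin toss". For the mandible, "split-mouth or same side surgical instrumentations will be performed, as described for maxilla". The plan sets no minimum distance between the two sites, no limit on the number of adjacent pairs, and no stratification by pair type.

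Under Primary Outcome Measures, "All ridge dimensions will be measured immediately after flap reflection and after final osteotomy preparation", at the crest and at two deeper levels. Readings are taken at a mark on the surgical guide showing the middle of the osteotomy: "the ridge dimensions will be measured using the mark as a standard reference". On timing there is one further sentence: "The measurements will be completed the day of surgery only".

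General Information gives the expected mechanism: "osseodensification drilling compacts and auto-grafts bone at the osteotomy walls resulting in increase of ridge dimension".

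The analysis, under Surgical technique and again under Statistics & Computer tomography analysis, is the paired t-test. It has no term for pair type or drilling order, and the plan does not ask for either to be recorded.

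**The concern.** A paired comparison of two sites in one mouth assumes that treating one site does not alter the outcome at the other. With sites on opposite sides of the mouth that is easy to accept. With adjacent sites it is less secure, because the test treatment is expected to widen the ridge and the control outcome is the width of the ridge next to it.

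The timing leaves the control site open to this. Its baseline is taken when the flap is raised, so it can precede all drilling at both sites. If the OD site is then drilled before the SD site's second reading, the SD change contains whatever expansion has reached it from the neighbour.

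The direction is clear even though the size is not. The SD change goes up, the OD change is untouched, and the difference moves toward zero. The plan's hypotheses are stated as no increase with OD, so the error favours keeping the null on the primary outcome. Pooling exposed and unexposed pairs in one t-test hides the problem, and drilling order cannot be recovered later if it was not written down.

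**Working it through.** **Inputs from the documents.** There are 20 patients with one OD and one SD site each; adjacent pairs are allowed; the baseline follows flap reflection; the second reading follows the osteotomy; no order is fixed; all pairs are pooled in a paired t-test. The plan gives no power, alpha, target difference or standard deviation for the paired difference, so there is no stated figure to reproduce.

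**Inputs not in the documents (all assumed).**
- f: share of the 20 pairs that are adjacent. Set at 0.5.
- q: share of adjacent pairs in which the OD site is drilled between the two SD readings. Set at 0.5 (order falls evenly and each site is read after its own osteotomy) or 1 (OD always drilled first, or both sites read at the end).
- s: spillover into the SD site as a fraction of the true OD-SD difference D. Set at 0.10 to 0.50.

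**Which orders create the bias.**
- SD drilled and read before OD drilling starts: no bias.
- OD drilled first, SD baseline already taken: the SD change includes spillover.
- OD drilled first, SD baseline taken afterwards: the spillover is mostly removed from the SD change. The plan instead places the baseline right after flap reflection.

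**Formula.** An unexposed pair has expected difference D. An exposed pair has D - sD. Averaging over pairs:

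(1 - q·f)·D + q·f·(1 - s)·D = D·(1 - q·f·s)

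**Results with f = 0.5.**

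| q | s | q·f·s (share of effect lost) | Retained |
|---|---|---|---|
| 0.5 | 0.10 | 0.025 | 97.5% |
| 0.5 | 0.50 | 0.125 | 87.5% |
| 1 | 0.10 | 0.05 | 95% |
| 1 | 0.50 | 0.25 | 75% |

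**Power, as illustration only.** Take a two-sided 5% paired t-test with 20 pairs and a standardised paired difference of 0.66, a value chosen because it gives 80% power without spillover. Multiplying 0.66 by the retained share gives power of 78% (s = 0.10) to 69% (s = 0.50) for q = 0.5, and 76% to 56% for q = 1. The 80% starting point is an assumption, not a property of this plan.

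**Can the data show the problem?** Suppose 10 adjacent and 10 split-mouth pairs, with q = 1 and s = 0.5. The gap between pair types is then 0.5 × 0.66 = 0.33 standard deviations. A two-sample t-test of 10 against 10 has about 11% power to detect it. A test by pair type could not settle the matter.

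**Would dropping adjacent pairs be better?** On the same 0.66 basis, keeping only split-mouth pairs gives 66% power with 15 pairs and 46% with 10. Re-timing the readings is far cheaper.

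**The case against.** The strongest reply is that the documents contain no evidence of carry-over. General Information places the OD effect at the osteotomy walls, each reading is taken at the centre of its own site, and no change at a neighbouring site is reported anywhere. This stands as a limit on size: spillover is possible under the plan, not demonstrated. The guide mark fixes where the reading is taken, but it does not isolate that point from movement of the ridge beside it.

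A reader might infer substantial carry-over from the 2.83 mm mean expansion in Background Information. The documents do not support that. The figure describes ridges only 1-3 mm wide at the crest, the group with the greatest gain, and it says nothing about how far expansion travels along the ridge. Nor does it support a claim of lost power. With the quoted SD of 0.66 mm and an assumed zero correlation, the paired SD is 0.66 × √2 = 0.93 mm and the standardised effect about 2.83 / 0.93 = 3.0, so power stays near 100% even if half the effect is lost.

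A reader might also take every adjacent pair as exposed, so that 5% to 25% becomes the general range at f = 50%. That is the q = 1 case. Objectives speaks of measuring before and after completion of the osteotomy, which is naturally read as each site after its own. The plan nowhere says that both sites are read at the end, or that adjacent sites share one flap. The exposure that remains is OD drilled first with the SD baseline already taken, and nothing in the plan excludes it.

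Finally, exposure may differ by jaw. Surgical technique sets clockwise drilling in the mandible, and the attached drill chart labels clockwise as cutting mode, so mandibular pairs may have less expansion to pass on. A single s for all adjacent pairs may therefore overstate the effect.

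**Conclusion.** The concern holds in a limited form. Following the plan as written can put a neighbour's OD expansion into the SD change, and this biases the pooled primary difference toward zero. It requires an adjacent pair, OD drilling between the two SD readings, and some spread of expansion along the ridge. The first two are left open by the plan; the third is unquantified.

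The loss is q·f·s of the true difference. It depends wholly on assumed values, and no single figure should be quoted as the expected loss. Because the error runs toward no effect, it would not by itself produce a false claim of benefit; it would understate OD or make a null finding harder to interpret. The change is worth making because it is cheap and the readings cannot be taken after the day of surgery.

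**What to change.** For adjacent pairs, state in Primary Outcome Measures that ridge width is read at each site immediately before its own osteotomy and again immediately after it, before work starts on the neighbouring site, and that this change is the primary value. Keep the reading after flap reflection as well. At an SD site drilled second, the shift between that reading and the one just before its osteotomy gives a direct, if noisy, look at spillover.

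Record drilling order and pair type (split-mouth or adjacent) for every patient. Report the primary difference by pair type descriptively, without a test, because 20 pairs cannot test it.

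The cost is a few extra caliper readings in adjacent pairs and one descriptive table. Eligibility, sample size and the choice of which site is drilled first are unchanged, although one osteotomy must be finished and read before the other begins. Two limits remain. Re-taking the baseline does not undo any change already made to the bone in which the second osteotomy is cut. Spillover into a site already read is not captured, which is acceptable for an outcome meant to describe each site's own preparation.
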